Effects of a high-intensity interval training (HIIT) exercise intervention on sleep quality in
women exposed to trauma: A randomized controlled trial

Date: 9/16/2021

Methods

C.2 Research design. A randomized control trial design will be used. Participants will be randomly assigned to one of the two treatment arms in blocks of two to optimize statistical power and minimize potential bias (Spieth et al., 2016). Sequentially numbered sealed envelopes created by a third-party using research randomizer (www.randomizer.org) will be used to allocate participants to treatments.

C.3 Participants. Seventy-two women who meet the inclusion criteria will be invited to participate. The seven inclusion criteria are: (i) exposure to a traumatic event, (ii) persistent PTSD-related symptoms adequate to screen positive for PTSD (Posttraumatic Diagnostic Scale-5 total scores > 27), (iii) poor sleep quality (Pittsburgh Sleep Quality Index >5), (iv) failure to meet recommended level of physical activity for U.S. adults (<150-mins of moderate or 75-mins of vigorous physical activity [or a combination] per week), (v) able to safely perform high intensity exercise (no contraindications based on the Physical Activity Readiness Questionnaire), (vi) aged 18-39 years, (vii) a non-smoker, (viii) willing to avoid alcohol and vigorous physical activity 24 hours before visiting the lab, and (ix) willing to avoid caffeine for 12 hours before visiting the lab.

C.4 Recruitment.

Several recruitment approaches will be implemented to ensure the required sample size is obtained. These approaches included: (i) e-mails sent to selected campus listservs, (ii) recruitment announcements in college classrooms, (iii) flyers placed in the University Health Center and around town, (iv) public service announcement made over the radio, and (v) by word of mouth.

C.5 Online Screening. Individuals interested in volunteering will be screened for eligibility by completing online surveys presented using Qualtrics. Eligible individuals will be invited to visit the Exercise Psychology Laboratory.

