Cardiac Vagal Tone: Each participant will place a bioharness monitor on in a private room. The R-R waveform will be sampled at 1000 hertz. Fast Fourier transformation will be applied, spectral power will be determined, and the average of the frequency domain will be calculated using Kubios analysis software (Tarvainen, Niskanen, Lipponen, Ranta-aho, & Karjalainen, 2014). After the frequency units from the heart cycles are converted to hertz, the vagal tone (high frequency band; 0.15-0.5 Hz), sympathetic tone (low frequency band; 0.05-0.15 Hz) and total power (0.017-0.5 Hz) will be calculated. The *apriori* focus is on changes in vagal tone.

Arithmetic Stress Task: Vagal tone will be measured at rest and during a stressor involving math calculations. Serial subtraction will be administered by a research team member dressed in white lab coat, with a clip board and pen for making notes. The team member will correct participants every time an incorrect answer is given and prompt participants to increase their pace every 15 seconds. Serial subtraction will involve sequentially subtracting 13 from a 4-digit number, and if an incorrect response is given, they will be asked to start over. The subtraction task will last a total of 10 minutes.

D.1.1 Expected Results. Based on our review of exercise training studies (McGranahan & O'Connor, 2021), we hypothesize HIIT to result in a clinically meaningful, moderate-sized or greater improvement in sleep quality. It is hypothesized that exercise-training induced changes in vagal tone will mediate the improvements in sleep quality. We do not expect improvements for sleep quality or vagal tone in the control group.

D.1.2 Statistical Power. A sample of 60 total participants will provide statistical power of 80%, at an alpha of 0.05. Assuming a moderate-sized interaction effect of 0.47 on sleep quality and a correlation of 0.85 between repeated measurements, the calculated sample size is 30 per group. Meta-analyses of participant drop out in exercise training trials shows that an average of 20% in the exercise groups and 15% in the control groups drop out (Kelley & Kelley, 2013). Using 20% attrition, recruiting 36 per group will result in 30 completers per group. The short-term (six-week) training duration should result in less than 20% compared to the meta-analysis which included primarily longer-term trials.

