D.1.3 Statistical Analysis. ANOVA will examine the effect of exercise training on sleep quality. Mediation of the effect by the change in vagal tone will be tested by adding the variable as a covariate to the model. A change in the significance of the f-value would indicate significant mediation (Baron & Kenny, 1986; Fiske, Kenny, & Taylor, 1982). To quantify the effect size exercise training has on sleep quality at weeks 2, 4, and 6 and vagal tone at baseline and post, Hedges' d will be calculated.

D. 2.0 Specific Aim 2. Evaluate the impact of six-weeks of high intensity interval training on sleep quality, statistically testing for the effect of the change in trait anxiety and hyperarousal symptoms.

State and Trait Anxiety Inventory: Trait anxiety will be used and is reduced after exercise training (J. W. Whitworth et al., 2019a).

The Posttraumatic Diagnostic Scale-5 (PDS-5): Hyperarousal symptoms will be measured using the hyperarousal subscale of the Posttraumatic Diagnostic Scale-5 (PDS-5). The full 24-item scale also will be used as part of the inclusion criteria to assess PTSD symptoms in the past month based on the diagnostic criteria for the DMS-5. The full PDS-5 assesses trauma history, symptom onset, and index of trauma. Internal consistency of the full PDS-5 and the hyperarousal subscale ≥ 0.90 .

D.2.1 Expected Results. Hyperarousal and anxiety symptoms are expected to decrease after HIIT and be correlated with improvements in sleep quality.

D.2.2 Statistical Analysis. A time-varying covariate analysis will determine if sleep quality changes are explained by the change in trait anxiety or hyperarousal at weeks 2-, 4-, or 6- of the intervention (Winer, 1991). To quantify the effect size exercise training has on PTSD symptoms and anxiety at weeks 2, 4, and 6, Hedges' d will be calculated.

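### The trial is sized on completers, and the plan names no analysis population, no missing-data method and no outcome collection after a woman stops training

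*Combined protocol and SAP*

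**What the plan says.** All places are in the combined protocol and SAP.

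- **C.3** sets the recruitment figure: "Seventy-two women who meet the inclusion criteria will be invited to participate".
- **D.1.2** gives the target, "A sample of 60 total participants will provide statistical power of 80%, at an alpha of 0.05", and its basis, with the number referring to each arm: "Assuming a moderate-sized interaction effect of 0.47 on sleep quality and a correlation of 0.85 between repeated measurements, the calculated sample size is 30". It cites a meta-analysis in which "an average of 20% in the exercise groups and 15% in the control groups drop out", and concludes: "Using 20% attrition, recruiting 36 per group will result in 30 completers per group". It then predicts better retention here: "The short-term (six-week) training duration should result in less than 20% compared to the meta-analysis which included primarily longer-term trials". Neither dropping out nor completing is defined.
- **D.1.3** tests the effect on sleep quality by ANOVA. It names no analysis population and no method for missing PSQI scores.
- **D.2.2** plans Hedges' d: "To quantify the effect size exercise training has on PTSD symptoms and anxiety at weeks 2, 4, and 6".
- **C.6** repeats the symptom measures every two weeks and at the end of week 6. It does not say whether this continues for a woman who has stopped training.
- **C.5** screens volunteers by "completing online surveys presented using Qualtrics", so an online survey platform is already in use.

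No section provides for recording why a woman stopped.

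**The concern.** A randomised comparison estimates the effect of being assigned to HIIT only if the women assigned are the women analysed. Here the sample size is built on those who finish, and the analysis section does not say what happens to the rest. A conventional repeated-measures ANOVA uses complete cases, so a woman with no post-intervention PSQI would be left out by default.

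That default does little harm if stopping is unrelated to outcome. It matters if women stop HIIT because they are not improving or feel worse. The mean of the remaining women would then look better than the mean of all women assigned, with nothing comparable in the waitlist arm, which has no training to stop. Such loss is plausible: C.3 enrols insufficiently active women who screen positive for PTSD, and C.7 raises the intensity each week and lengthens the intervals from week 3. Data not collected when a woman stops cannot be recovered at the analysis stage.

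**Working it through.** **1. The plan's own figures (D.1.2).** Inputs: 30 per group needed, 20% attrition, 36 per group recruited.

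- 30 × 1.2 = 36 reproduces the recruitment figure, but 36 × (1 − 0.20) = 28.8, not 30. Going from 36 to 30 is a loss of 6/36 = 16.7%. Allowing for 20% loss needs 30/0.8 = 37.5, so 38 per group.
- The 30 per group cannot be reproduced, because the metric of the 0.47 is not defined. If it is in raw SD units with r = 0.85, a change score has SD √(2 × 0.15) = 0.548. Two-sided power at 30 per group is then Φ(0.47/(0.548 × √(2/30)) − 1.96) = Φ(1.36) = 91%. If it is in change-score SD units, power is Φ(0.47/√(2/30) − 1.96) = Φ(−0.14) = 44%.

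These are separate matters. They are noted because the 0.47 is used below as a standardised mean difference, which is an assumption.

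**2. How many women are involved.** At the cited averages, 36 × 0.20 = 7.2 in HIIT and 36 × 0.15 = 5.4 on the waitlist, a difference of 1.8. D.1.2 expects attrition below 20% but gives no figure, so 10% is used as an assumed lower value.

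**3. Effect of assignment against effect in completers.** Let p be the share of the HIIT arm who stop, and s their mean change relative to controls, in SD units (positive means improvement). With 0.47 in completers and no change in controls:

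E = (1 − p) × 0.47 + p × s; overstatement = 0.47/E − 1.

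| p | s = 0 (no gain) | s = −0.5 (assumed worsening) |
|---|---|---|
| 10% | 0.9 × 0.47 = 0.423; 11% | 0.423 − 0.05 = 0.373; 26% |
| 20% | 0.8 × 0.47 = 0.376; 25% | 0.376 − 0.10 = 0.276; 70% |

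At p = 20%, s = −0.25 gives 0.376 − 0.05 = 0.326, and s = −1.0 gives 0.376 − 0.20 = 0.176. If those who stop do as well as completers (s = 0.47), E = 0.47 and there is no bias.

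**4. What analysing everyone does to power.** Take all 36 per group and E = 0.376, with outcome SD unchanged. On the raw-SD reading, power is Φ(0.376/(0.548 × √(2/36)) − 1.96) = Φ(0.95) = 83%. On the change-SD reading it is Φ(0.376/√(2/36) − 1.96) = Φ(−0.36) = 36%. Which applies depends on the undefined metric in step 1.

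**The case against.** The strongest reply is that the plan never says it will exclude anyone. The sentence about 36 and 30 per group is a recruitment allowance, and D.1.3 does not restrict the ANOVA to completers. D.1.2 also applies dropout to control groups, where it can only mean leaving the study. Both points stand. A reader might infer that the plan counts women who leave training as lost and discards them. The documents do not say so; the risk comes from silence combined with the usual behaviour of ANOVA.

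Three other inferences should also be resisted.

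- **That the plan expects 20% and 15% loss.** These are averages from a cited meta-analysis. The plan applies 20% to both arms and expects less.
- **That women who worsen vanish from the harm results.** The sections available describe no adverse-event or harm analysis for anyone, so there is nothing to vanish from. The two-weekly symptom measures in C.6 may also capture a woman before she stops.
- **That women will stop because symptoms or sleep deteriorate.** No section gives reasons for stopping.

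Withdrawal wording may exist in pages not available for review. The power and analysis sections are present, however, and they leave the question open. The reply limits how strongly the point can be put but does not close the gap.

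**Conclusion.** The point holds as a gap in the plan, not as a stated exclusion. Followed as written, with a conventional ANOVA, the plan would analyse women who have a post-intervention score and would be open to bias from outcome-related dropout.

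Under the illustration, a completer effect of 0.47 corresponds to an effect of assignment of 0.42 to 0.38 if 10% to 20% stop without gain, and 0.37 to 0.28 if they worsen by 0.5 SD. These figures rest on four assumptions: 0.47 is a standardised completer effect, controls do not change, the share stopping is 10% to 20%, and those who stop respond as specified. They show how large the bias could be and do not predict it. If stopping is unrelated to response, there is none.

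The change is worth making because it is cheap and the missing data cannot be obtained later.

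**What to change.** - **C.6 and C.7:** state that any participant, in either arm, who stops training or laboratory visits stays in the study unless she withdraws from it. Ask her to complete the PSQI, PDS-5 and trait STAI at the remaining week 2, 4 and 6 time points, online if she will not attend. Record the mode of collection and the reason for stopping. C.6 places sleep measurement at baseline and post only, while D.1.3 uses weeks 2, 4 and 6; reconcile these at the same time.
- **D.1.3:** analyse all randomised women as assigned, using all available scores (a mixed model for repeated measures would do this). Make any completer analysis secondary.
- **D.1.2:** define a completer as a woman with outcome data obtained, not one who finished training.
- **Reporting:** give by arm the number who stopped (training in the HIIT arm, visits in either arm) and why. Do not add a count of women scoring worse than baseline at any visit unless a worsening threshold is set in advance; without one, it would mostly reflect measurement noise.

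The cost is protocol wording and survey links for about 7 + 5 = 12 women at the cited rates, on a platform already used for screening. There are two downsides. The estimated effect may be smaller, and some questionnaires will be completed online instead of in the laboratory, possibly unequally between arms, which is why the mode is recorded.

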C.6 Baseline and Post-intervention. Prior to the testing, individuals will be asked to avoid alcohol consumption and moderate to vigorous physical activity 24 hours prior. Following the informed consent process, individuals will complete a brief menstrual history, 24-hour health status recall, and provide a saliva sample. Information about potential confounders and psychological symptoms also will be obtained using standardized methods supported by evidence of their validity (i.e., measures of symptoms of depression and anxiety, anxiety sensitivity, and physical activity history). These assessments will be repeated every 2 weeks and at the end of the six-week experiment. A body composition assessment via a dual-energy x-ray absorptiometry (DXA) will be completed. In a private room, the participants will fasten a wireless Zephyr™ BioHarness™ (Zephyr Technology, Auckland, New Zealand) below the sternum, (see figure 3). The Zephyr™ BioHarness™ will assess autonomic function via variability in heart rate. A baseline heart rate variability will involve adopting a seated position and measuring ECG while the participants rest for 5 minutes. Participants will complete the state portion of the State-Trait Anxiety Inventory (STAI), followed by a mental arithmetic task in which the participant will subtract by 13 from a 4-digit number for 10 minutes. Immediately after the mental arithmetic, participants will complete the state portion of the STAI. Participants will then complete a seated recovery for 5 minutes. Next, peak oxygen uptake (VO_{2Peak}) and peak power output (PPO) will be measured via a ramped bicycle protocol (Lode Excalibur Sport). Power output will be increased by 15 watts every minute until volitional exhaustion. Expired gases will be continuously measured via indirect calorimetry (Parvo Medics TrueOne 2400;

Parvo Medics, Salt Lake City, UT), and heart rate will be continuously monitored throughout the exercise test via a chest heart monitor (Polar; Polar Electro Inc., Lake Success, NY). The VO_{2peak} test will be administered so that participants can be prescribed the same exercise intensity, relative to their PPO, during exercise training. Saliva, DXA, vagal tone, peak oxygen uptake (VO_{2peak}), and sleep will be measured at baseline and after the six-week intervention.

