C. 7 High-Intensity Interval Training (HIIT). HIIT participants will complete three leg cycle ergometer bouts weekly. During the first two weeks, the participants will complete 13, 30-second high intensity exercise intervals at a wattage prescribed to elicit 67% of PPO. Each 30-second exercise interval will be followed by a 1-minute active recovery interval at 30% of PPO. Each week, prescribed wattage will be increased by 4% of PPO. Thus, in the final week, the training intensity will be at 87% of PPO (See table 1 for training example). At the start of the third week, the exercise duration will be increased. Specifically, the 13, 30-second-high intensity intervals will increase to 10, 60-second high intensity intervals. All sessions will start with a three-minute warm-up and end with a two-minute cool-down on the cycle ergometer. In sedentary panic disorder patients, a 12 day HIIT training intervention of similar initial exercise intensity was well tolerated and showed rapid reductions in symptoms (Plag, Ergec, Fydrich, & Strohle, 2019). During the exercise sessions, ratings of perceived exertion, quadriceps pain, and heart rate during the exercise sessions will be assessed 0, 5, 10, 15, 20 minutes into the HIIT.

C.7 Waitlist Control (WL). Participants randomly assigned to the waitlist will visit the laboratory in order to complete the baseline, bi-monthly assessments and post-assessments. They will be asked to maintain their current lifestyle. They will be given the option to receive a six-week supervised HIIT training program after the waitlist participation.

D. Primary Outcome Measures for the Specific Aim

D.1 Specific Aim 1. Evaluate the impact of six-weeks of high intensity interval training on sleep quality and whether the effect is accounted for by the change in vagal tone.

Pittsburgh Sleep Quality Index-(PSQI): The PSQI is the gold standard measure of self-reported sleep quality. It consists of 19 items. Scores range from 0-21, higher scores indicate poorer sleep quality. A global score ≥ 5 indicates poor sleep quality with a sensitivity of 0.90 and specificity of 0.87 compared to polysomnographically determined poor sleep (Buysse et al., 1989). The PSQI instructions will be modified to better assess rapid changes in usual sleep habits (last two weeks rather than the past month).

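### C.6 and D.1.3/D.2.2 disagree on when sleep is measured, and the Aim 1 ANOVA does not use the already collected baseline PSQI as a covariate

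*Combined protocol and SAP*

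**What the plan says.** **Sleep visits.** The closing sentence of C.6 lists several measures "and sleep will be measured at baseline and after the six-week intervention". Earlier in C.6, after a list of confounders and psychological symptoms that does not name sleep, the protocol says "These assessments will be repeated every 2 weeks and at the end of the six-week experiment". D.1.3, by contrast, plans Hedges' d as follows: "To quantify the effect size exercise training has on sleep quality at weeks 2, 4, and 6". D.2.2 asks whether "sleep quality changes are explained by the change in trait anxiety or hyperarousal at weeks 2-, 4-, or 6". Under Specific Aim 1 the PSQI recall window is changed to the "last two weeks rather than the past month". The PSQI is the only sleep instrument described.

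**Primary test.** Aim 1 reads "Evaluate the impact of six-weeks of high intensity interval training on sleep quality and whether the effect is accounted for" by vagal-tone change. The whole description of its test is "ANOVA will examine the effect of exercise training on sleep quality". The one covariate named belongs to the mediation step: "Mediation of the effect by the change in vagal tone will be tested by adding the variable as a covariate to the model". D.1.2 bases the sample size on an interaction effect of 0.47 and a correlation of 0.85 between repeated measurements, with 30 per group for 80% power at alpha 0.05. It gives neither the number of measurements nor the units of 0.47.

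**The concern.** The schedule matters first. If PSQI is collected only at the two occasions named in C.6, the week-2 and week-4 effect sizes in D.1.3 have no data behind them. D.2.2 very likely fails as well, unless it was meant to relate a single baseline-to-week-6 sleep change to covariates at several weeks.

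The schedule also determines the Aim 1 test. A two-visit interaction asks whether the change from baseline to week 6 differs between groups. A four-visit interaction asks whether the groups differ anywhere in the pattern over time. These are different questions, and Aim 1 concerns the effect of six weeks of training.

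Finally, baseline PSQI is in hand for every woman, since it is an entry criterion. Adjusting the week-6 comparison for it would give a more precise answer to Aim 1 at almost no cost, and D.1.3 does not do so.

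**Working it through.** **Inputs.** From D.1.2: effect 0.47, correlation r = 0.85, n = 30 per arm, alpha 0.05, target power 80%. Assumed: two-sided testing; 0.47 in raw-score SD units, with a second reading below; and, for four visits, compound symmetry (the same correlation between every pair of visits).

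**Degrees of freedom.** Interaction df = (groups − 1)(visits − 1). Two visits: 1 × 1 = 1. Four visits: 1 × 3 = 3.

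**The plan's own figure.** The two-visit interaction needs 23 per arm for 80% power and has 90.5% at 30 per arm, so it does not reproduce 30 per arm for 80%. The four-visit interaction comes close if the effect builds gradually: 28 per arm for linear onset, 31 if half the effect is present at weeks 2 and 4. The plan states no such time course, so this does not show which test was meant.

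**Two-visit interaction (change score) against baseline-adjusted week 6.** Variance of the group difference, in squared SD units:

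- Change score: 4(1 − r)/n = 4 × 0.15/30 = 0.0200; SE 0.141; 0.47/0.141 = 3.32; power 90.5%.
- Baseline-adjusted: 2(1 − r²)/n = 2 × 0.2775/30 = 0.0185; SE 0.136; 0.47/0.136 = 3.46; power 92.5%.
- Variance ratio: 0.0185/0.0200 = 0.925, which is (1 + r)/2. For 80% power, 21 against 23 per arm.

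Power is from the noncentral t. A simulation of 40,000 trials with linear onset gave 92.1% against 90.2%, so the gap does not depend on the formula.

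**Sensitivity.**

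| Setting | Baseline-adjusted | Change score |
|---|---|---|
| r = 0.85, raw-score SD units | 92.5% | 90.5% |
| r = 0.70 (assumed), raw-score SD units | 71% | 64% |
| r = 0.85, change-score SD units | 46% | 43% |

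For r = 0.70 the variances are 2 × 0.51/30 = 0.034 and 4 × 0.30/30 = 0.040. In the last row the raw effect is 0.47 × √0.30 = 0.257.

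**Four-visit interaction.** λ = (n/2) Σ(e − ē)²/(1 − r), where e is the group difference at each visit; F with 3 and 3 × 58 = 174 df. Here (30/2)/0.15 = 100, and 0.47² = 0.2209.

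| Share of effect at baseline, weeks 2, 4, 6 | λ | Power |
|---|---|---|
| 0, ½, ½, 1 | 11.05 | 80% |
| 0, ⅓, ⅔, 1 (linear) | 12.27 | 84% |
| 0, 1, 1, 1, or 0, 0, 0, 1 | 16.57 | 94% |
| 0, 0, 1, 1 | 22.09 | 98% |

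Under these assumptions, 80% and 98% are the lowest and highest values over all non-decreasing patterns that reach the full effect at week 6. With complete data the week-6 contrast from a mixed model with baseline and baseline-by-week terms has the same standard error as the ANCOVA, so 92.5% applies to both.

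**The case against.** **The interaction already uses baseline.** This stands. A reader might infer from D.1.3 that the primary analysis ignores baseline PSQI, comparing week-6 scores alone and losing much of the power. The documents do not support that: D.1.2 speaks of an interaction and of correlated repeated measurements, and that correlation would play no part in a week-6-only comparison. The fair comparison is with the change score, where the gain at the plan's r is 2 points and both tests exceed 80%.

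**The four-visit test may be the stronger one.** This also stands for some onset patterns. C.7 lengthens the exercise intervals from week 3, so an effect complete by week 4 cannot be ruled out, and there the 3-df test has 98%. The case for the week-6 contrast is that it answers Aim 1, not that it always has more power. The 80% to 98% range is itself conditional: a multivariate test gives 77.5% for the first pattern. With correlation that decays between visits (baseline to week 6 still 0.85), the uncorrected 3-df test reached about 92% rather than 84% under linear onset, with type I error near 6.5%.

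**The effect metric is open.** If 0.47 were Cohen's f, both tests would have close to 100% power and the precision argument would vanish.

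**The conflict leans towards four visits.** D.1.3, D.2.2, the two-week recall and the two-weekly assessments point the same way, against one sentence in C.6. The correction may therefore be small, but until it is made staff following C.6 would not collect the interim PSQI. An ANOVA of weeks 2, 4 and 6 alone would have 2 df, but D.1.2 does not point to it.

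**Test selection.** A reader might infer that the loose wording invites choosing the test after seeing the data. Nothing in the documents suggests that intention, and no inflated error rate is claimed.

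**Conclusion.** The point holds as a cheap improvement, in two parts.

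First, the schedules conflict. If C.6 governs, the week-2 and week-4 sleep effects in D.1.3 cannot be computed, and D.2.2 very probably cannot be run as described. This rests on the text alone, plus the observation that no sleep measure other than the PSQI is described.

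Second, the Aim 1 test can be made more precise, and independent of the number of visits in what it estimates, by adjusting week-6 PSQI for baseline. At the plan's r = 0.85 and with 0.47 in raw-score SD units, this removes 7.5% of the variance of the two-visit interaction estimate. The power gain is 2 points there, about 7 points if r were 0.70, and about 3 points if 0.47 is in change-score SD units. Against the four-visit interaction it can gain or lose power.

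The trial remains analysable either way. The unstated analysis set, missing-data rule and effect-size units are missing detail, not separate defects, and the mediation method is not part of this point.

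**What to change.** 1. Reconcile C.6 with D.1.3 and D.2.2 on whether PSQI is collected at weeks 2 and 4.

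2. Replace the first sentence of D.1.3 with:

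> The primary test is the group difference in week-6 PSQI, adjusted for baseline PSQI, with 95% CI, in women analysed in the group assigned.

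Then name the model that matches the schedule:

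- Two visits: ANCOVA of week-6 PSQI on group and baseline PSQI.
- Four visits: the week-6 contrast from a mixed model of PSQI at weeks 2, 4 and 6 with group, week, group-by-week, baseline PSQI and baseline-by-week. The joint test over weeks is secondary.

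**Cost.** SAP wording and standard software. If PSQI is not yet planned at weeks 2 and 4, the four-visit option adds a short questionnaire to assessments that C.6 already repeats every two weeks.

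**Downsides.** For some onset patterns the week-6 contrast has less power than the 3-df test (92.5% against 98% if the effect is complete by week 4). The mixed model assumes data are missing at random. The two-visit ANCOVA uses only women with a week-6 PSQI.

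### Mediation by vagal tone is judged by whether the F-value changes significance, which does not test the indirect effect

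*Combined protocol and SAP*

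**What the plan says.** Specific Aim 1 (D.1) has two halves: the effect of six weeks of HIIT on sleep quality, and "whether the effect is accounted for by the change in vagal tone". D.1.1 makes the second half a hypothesis: "It is hypothesized that exercise-training induced changes in vagal tone will mediate the improvements in sleep quality".

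D.1.3 gives the analysis. The base model is brief: "ANOVA will examine the effect of exercise training on sleep quality". Then: "Mediation of the effect by the change in vagal tone will be tested by adding the variable as a covariate to the model". The decision rule is one sentence: "A change in the significance of the f-value would indicate significant mediation".

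The only other analysis of vagal tone in D.1.3 is an effect size: "vagal tone at baseline and post, Hedges' d will be calculated". The time-varying covariate analysis in D.2.2 concerns trait anxiety and hyperarousal. No section specifies an estimate, interval or test of the indirect effect, or a test of either path that makes it up.

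**The concern.** Mediation means that training changes vagal tone (path a) and that vagal tone, given group, changes sleep (path b). The quantity of interest is a×b. The rule looks instead at whether the group effect lies on the same side of 0.05 before and after adjustment. Hedges' d describes path a and the adjusted model yields a coefficient for b, but neither enters the decision. Three faults follow.

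1. **False mediation.** If training moves vagal tone but vagal tone does nothing for sleep, the covariate is still correlated with group. The standard error of the group effect rises, and significance can be lost for that reason alone.
2. **Missed mediation.** If mediation is real but partial, the direct effect may stay significant. If the total effect was not significant to begin with, there is no significance to lose.
3. **No stated direction.** Aim 1 implies loss of significance, but read literally an F-value that becomes significant would also count.

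At stake is the conclusion on mechanism, which is half of Specific Aim 1 and has no other decision rule.

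**Working it through.** **The plan's own figure.** D.1.2 gives 30 completers per group, 80% power and alpha 0.05, with these inputs: "Assuming a moderate-sized interaction effect of 0.47 on sleep quality and a correlation of 0.85 between repeated measurements". It gives no power for the mediation test. If 0.47 is in SD units of the score and the analysis is of pre-post change, the SD of change is √(2(1 − 0.85)) = √0.30 = 0.548, and the effect is 0.47/0.548 = 0.858 SD of change. The normal approximation, two-sided, gives 2 × (1.960 + 0.842)²/0.858² = 21.3, so 22 per group (23 by t), with power 0.91 at 30. Adjusting for baseline instead gives 20 (21 by t), and ignoring the correlation gives 72 (73 by t). A group-by-time F test over four time points gives 21 to 31 across five assumed time profiles. The plan states neither the metric nor the time points, so 30 can be neither confirmed nor called wrong. Two totals are therefore carried forward: 0.858, and 0.736, which has 80% power at 30 per arm.

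**Model.** M = a·group + e₁ and D = (total − a·b)·group + b·M + √(1 − b²)·e₂, with D the change in sleep score and within-group SDs of 1. There are 30 per arm and 20,000 trials per scenario, so the Monte Carlo standard error of the rule's rates is at most √(0.25/20,000) = 0.35 percentage points. D is regressed on group, then on group and M. The rule fires when p < 0.05 becomes p ≥ 0.05. The comparator is a 95% Monte Carlo interval for a×b. The values of a and b are assumptions.

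**No mediation (b = 0).**

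| a (SD) | Rule, total 0.858 | Rule, total 0.736 | Interval, total 0.858 |
|---|---|---|---|
| 0 | 1.1% | 1.5% | 0.1% |
| 0.5 | 3.5% | 5.0% | 2.6% |
| 1.0 | 9.2% | 12.3% | 5.3% |
| 1.5 | 18.7% | 22.0% | 5.3% |

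The cause is variance inflation, which is 1 + a²/4 with equal arms. At a = 1.5 it is 1.56, so the standard error grows by √1.56 = 1.25. At total 0.858 the expected t falls from 0.858 × √15 = 3.32 to 3.32/1.25 = 2.66, closer to the critical value of about 2.00.

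**True partial mediation (a = 0.8, b = 0.5, a×b = 0.40 in every row).**

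| Total | Direct | Rule | Interval |
|---|---|---|---|
| 0.3 | −0.10 | 20% | 87% |
| 0.5 | 0.10 | 42% | 87% |
| 0.736 | 0.336 | 53% | 87% |
| 0.858 | 0.458 | 45% | 85% |
| 1.2 | 0.80 | 10% | 85% |

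The indirect effect is the same throughout, yet the rule's detection rises and then falls with the total effect. At 0.858 the indirect share is 0.40/0.858 = 47%. The direct effect has standard error √0.75 × √(2/30) × √1.16 = 0.241 and expected t of 0.458/0.241 = 1.90, so its significance is close to a coin toss.

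**Complete mediation (a = 1.43, b = 0.6, total 0.858).** The rule detects 87%, the interval over 99%.

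**Any-direction reading (a = 0, b = 0.5, so no mediation).** The rule fires in 6.9% of trials at 0.858 and 12.8% at 0.736, against 0.5% and 1.4% when only loss counts.

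**Baseline-adjusted model (post score on group, baseline and M), total 0.858.** False mediation is 1.1%, 2.9%, 8.6% and 17.4% at a = 0, 0.5, 1.0 and 1.5. True partial mediation is detected in 44% of trials, against 86% for the interval.

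**The case against.** - **The percentages rest on assumed paths.** The documents give neither a nor b. False mediation is at or below 5% for a up to 0.5 SD, and 6.6% to 8.5% at a = 0.8. The 19% needs training to move vagal tone by 1.5 SD, which the protocol does not predict. This stands as a limit on the size, not on the fault.
- **The interval is not powerful everywhere.** At total 0.736, rule against interval, detection is 27% against 49% (a = b = 0.5), 19% against 30% (a = 0.5, b = 0.3) and about 10% against 12% (a = b = 0.3). With 60 completers, small indirect effects will mostly be missed by either method. This stands, but it does not make the rule a test of a×b.
- **0.858 is a conversion.** At 0.736 detection is 53%, not 45%. Both values are shown, and the conclusion is the same.
- **The cited methods papers might add conditions on the paths.** If both paths also had to be significant, false mediation at a = 1.5 would fall to about 1.7%, but detection at a = 0.8, b = 0.5 and total 0.858 would be only about 42%. The plan writes no such condition, so an analyst following it would not apply one.
- **Direction is clear from context.** Largely so: Aim 1 points to loss of significance, and the any-direction figures deserve little weight.
- **A single pre-post contrast simplifies the planned ANOVA**, which D.1.3 leaves unspecified. That is so, but the fault lies in comparing two significance verdicts, whatever the number of time points.

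**Conclusion.** The concern holds. As written, the rule does not test the indirect effect, and its error rates are not controlled by design. The qualitative conclusion is firm. The sizes are illustrative and rest on 30 completers per arm, two-sided 0.05, one change score per person and assumed a and b. At the two totals linked to the protocol, an indirect effect of about half the total (0.40/0.858 = 47%; 0.40/0.736 = 54%) is found in 45% to 53% of trials, against 85% to 87% for an interval on a×b. False mediation becomes material once training moves vagal tone by about 0.8 SD or more. The rule performs better when mediation is nearly complete. The randomised effect on PSQI is untouched, so this should be fixed but does not threaten the main comparison.

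**What to change.** Replace the significance-change sentence in D.1.3 with an estimate of the indirect effect:

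1. Regress change in vagal tone on group (a).
2. Regress post-intervention PSQI on group, baseline PSQI and change in vagal tone (b and the direct effect). This is a baseline-adjusted model in place of the loosely specified ANOVA, and the text should say so. Using the same baseline covariates, including baseline vagal tone, in every regression lets a×b and the direct effect sum to the total.
3. Report a×b with a 95% bootstrap or Monte Carlo confidence interval, and conclude mediation only if it excludes 0.
4. Report a, b and the direct and total effects with intervals, whatever the verdict.
5. Word a positive result as consistent with mediation: the mediator is not randomised, and vagal tone and sleep change over the same six weeks.

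One separate gap can be closed in the same edit. D.1 says "Vagal tone will be measured at rest and during a stressor involving math calculations", so the plan should name which measure forms the change score.

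The cost is revised analysis-plan wording and a few lines of code. No new data or participants are needed.
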